5.6.3 Guidelines for Use of Factor IX for Subjects Undergoing Major Surgery

Replacement of factor IX for subjects undergoing major surgery in this trial will be according to established guideline (Srivastava et al., 2013) in terms of factor IX activity level pre and post-surgical procedure. The target factor IX activity level pre and post-major surgery regardless of whether the regular or extended half-life replacement is administered as per World Federation of Hemophilia is as follows:

	Factor IX Activity Level
Pre-operative:	60-80%
Post-operative:	40-60% Day 1-3
-	30-50% Day 4-6
	20-40% Day 7-14

For minor surgery, use of factor IX is up to the Investigator but should be discussed with the medical monitor.

Factor IX infusions are not recommended for subjects with factor IX activity in the non-hemophilic (\geq 40% of normal) range especially in subjects with a confirmed COVID-19 infection, as increased thrombogenic risk is a known complication of COVID-19. Subjects with factor IX activity in the non-hemophilic range post-treatment with AMT-061 and infected with COVID-19 may potentially be at the same risk of thrombosis as subjects without hemophilia; antithrombotic therapy for these subjects should be considered under the same guidelines recommended for those without hemophilia.

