transgene activity is approximately 6 times higher per unit protein for AMT-061 as compared to AMT-060. Although the study design only included a direct comparison at 5 x 10^{12} gc/kg, it can be expected that plasma exposure, liver distribution, liver cell transduction and transgene expression behave similarly at each dose level with a range. As expected, the study demonstrated that for the same dose, the mean factor IX protein of AMT-060 (average of 4.89, ranging from 3.17 to 7.61 %) and AMT-061 (average of 4.85, ranging from 2.92 to 6.17 %) was comparable. The confirmation of transgene activity being approximately six times higher per unit protein (average of 6.10, ranging from 5.41 to 7.47 %) can similarly be expected to result in multiple of the already demonstrated activity levels of AMT-060 within a range. These results are comparable to the increase in gain-of-function reported for the Padua factor IX protein compared with "wild-type" factor IX protein in animal models (Crudele et al., 2015; Monahan et al., 2015).

The observed translation of the NHP for AMT-060 to the clinical Phase 1/2 for AMT-060 supports the translation of the NHP study for AMT-061 (NR-061-17-001, Study No. NC1615) to further inform the dose rationale for the proposed dose confirmation trial with 2×10^{13} gc/kg AMT-061. At 2 x 10^{13} gc/kg, AMT-061 is predicted to result in mean factor IX activity ranges of 40% of normal, with acceptable ranges (between approximately 18-76%) within the expected safety for factor IX replacement with an upper range well below the cut off of 129%.

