3.2 Trial Design Rationale

In gene therapy it is common practice to provide a single dose of vector via IV infusion. This infusion in a previous trial with AMT-060 was proven to be safe and effective resulting in identification of a clincial dose for AMT-060 to proceed to further clinical studies. Although this resulted in successful conversion of clinical phenotype to mild in most subjects, the desired goal is to achieve higher levels of factor IX activity to allow for a more consistent and meaningful clinical response. This trial will investigate AMT-061 at the identified dose for AMT-060 ($2 \times 10^{13} \text{ gc/kg}$).

This is the first trial with the gene product AMT-061 in humans. As AMT-061 is an isolated modification of the wild-type human factor IX in AMT-060, it is expected that the safety of this product improvement will be similar as the safety characteristics that have been described for AMT-060 at a dose of 2×10^{13} gc/kg. Also, clinical benefit of AMT-060 was achieved at this dose (refer also to Section 1.4 for a description of the Phase 1/2 trial). Therefore, a similar dose of AMT-061 will be used in this trial. Based on NHP studies with AMT-061, as well as data from patients with the natural Padua mutation, it is expected that the modified product AMT-061 will lead to a higher level of circulating factor IX activity at comparable levels of factor IX protein and thereby increase the likelihood of alleviating the need for exogenous therapy,

including the need for on-demand treatment of traumatic bleeds and selective prevention of a bleed (e.g., because of upcoming physical activity, sports, etc.). At $2 \ge 10^{13}$ gc/kg, AMT-061 is expected to result in mean factor IX activity ranges of 40% of normal, ranging between approximately 18-76%.

This trial is conducted at multiple centers as the prevalence of severe and moderately severe hemophilia B subjects is low.

Due to the nature of the disease in question it is not ethical to perform a placebo-controlled trial and no relevant active comparators exist. Based on this the trial is designed as an open-label and uncontrolled trial.

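### Section 5.6.3 sets a 60-80% pre-operative factor IX target for major surgery, then advises against infusion at 40% or above without saying which text governs; the two collide for endogenous activity from 40% to under 60%

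*Protocol*

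**What the plan says.** Section 5.6.3 of the protocol opens with a directive: "Replacement of factor IX for subjects undergoing major surgery in this trial will be according to established guideline". It then introduces a table as "The target factor IX activity level pre and post-major surgery regardless of whether the regular or extended half-life replacement is administered". The table gives 60-80% before the operation, then 40-60% on days 1-3, 30-50% on days 4-6 and 20-40% on days 7-14. The one place where the section hands the choice to the site concerns smaller procedures: "For minor surgery, use of factor IX is up to the Investigator but should be discussed with the medical monitor".

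The closing paragraph of the same section begins "Factor IX infusions are not recommended for subjects with factor IX activity in the non-hemophilic" and sets the boundary at or above "40% of normal) range especially in subjects with a confirmed COVID-19 infection, as increased thrombogenic risk is a known complication of COVID-19". The same paragraph stands in section 5.6.2 (concomitant therapy) and section 6.2.2.1 (factor IX replacement therapy). None of the three copies mentions surgery as an exception.

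On expected activity, section 1.3.1 states that "AMT-061 is predicted to result in mean factor IX activity ranges of 40% of normal, with acceptable ranges (between approximately 18-76"%), and section 3.2 repeats the figures. The SAP contains no rule on peri-operative factor IX use.

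**The concern.** A site preparing a subject for major surgery would turn to section 5.6.3 and find a target to reach and, a few lines later, advice that may point the other way. If his endogenous activity is at or above 40% but below the pre-operative target, following the table means infusing against a stated thrombogenicity caution. Following the closing paragraph means operating below the stated target. Nothing in the section says which applies, so two sites could treat like subjects differently and both cite the protocol.

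The situation is foreseeable. The protocol has a section for major surgery, follow-up lasts five years, and the SAP plans a listing of on-study invasive procedures. In the ten-subject AMT-060 trial described in section 1.3.2.2, one serious adverse event was a myelopathy following surgery, and one subject's 135% rise in annualized factor IX use was attributed mainly to surgery.

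**Working it through.** This is a comparison of thresholds. No sample-size or power figure is involved.

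**Inputs.** Cut-off for the advice against infusion: 40% or above (5.6.3, closing paragraph). Target rows: 5.6.3 table. Predicted activity: mean 40%, range about 18-76% (1.3.1 and 3.2). Activity is taken as endogenous.

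**Step 1: is the plan's prediction plausible?** The protocol gives AMT-060 high-dose activity as a mean of 7.1%, with subject means from 3.1% to 12.7% (1.3.2.2), and a Padua gain of about 6-fold. Then 7.1 × 6 = 42.6, 3.1 × 6 = 18.6 and 12.7 × 6 = 76.2. These are close to the stated 40% and 18-76%, so I use the plan's figures.

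**Step 2: where do the texts conflict?** For endogenous activity *a* and a target row with lower bound *L*, the table calls for factor IX when *a* < *L*, and the paragraph advises against it when *a* ≥ 40. Both hold only when 40 ≤ *a* < *L*.

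| Row | Target | *L* | Conflict |
|---|---|---|---|
| Pre-operative | 60-80% | 60 | 40 ≤ *a* < 60 |
| Days 1-3 | 40-60% | 40 | none |
| Days 4-6 | 30-50% | 30 | none |
| Days 7-14 | 20-40% | 20 | none |

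**Step 3: spot values in the pre-operative row.**
- *a* = 39.9: needs a rise of 20.1 to 40.1 points; the advice does not apply; no conflict.
- *a* = 40: needs 20 to 40 points; the advice applies; conflict.
- *a* = 50: needs 10 to 30 points; conflict.
- *a* = 59.9: needs 0.1 to 20.1 points; conflict.
- *a* = 60: already within target; no conflict.

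**Step 4: how many subjects might be in the band?** The band is 60 − 40 = 20 points wide and the predicted range is 76 − 18 = 58 points, so 20/58 = 34% of the width. That is not a share of subjects. The documents give no distribution, so the following rests on an assumption: activity is lognormal with mean 40, and the ratio 76/18 spans the central 80%, 90% or 95% of subjects. The log-scale SD is s = (ln 76 − ln 18)/(2z), and the median is 40·exp(−s²/2).

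| Coverage assumed | s | Median | Share in 40 to <60% |
|---|---|---|---|
| 80% | 0.562 | 34% | 23% |
| 90% | 0.438 | 36% | 29% |
| 95% | 0.367 | 37% | 33% |

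With three subjects the expected number in the band is 3 × 0.23 = 0.7 to 3 × 0.33 = 1.0, before asking whether any of them has major surgery.

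**The case against.** The best defence is that the closing paragraph only advises. Section 5.6.2 lists the treatments that are not allowed. Factor IX for surgery is not among them, no other restriction is placed on concomitant treatment, and extra on-demand factor IX is permitted where judged necessary. A site that infused to the target would break no rule. The surgical text is also the more specific, and the paragraph looks like a general caution carried into three sections. This stands in part: a reader might infer two flatly opposite instructions, and the documents do not go that far. They set a directive beside contrary advice. But the paragraph is printed in the major-surgery section, directly after the surgical guidance, and nothing says that the specific text prevails. The amendment history links the added text to subjects with confirmed COVID-19, but the current wording is broader, and a change log does not govern conduct.

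A reader might also infer that the conflict falls on the typical subject. The documents do not show that. The predicted mean lies exactly on the cut-off, and under the assumption in the working the median is below it, with about two thirds to three quarters of subjects outside the band. Nor does the conflict extend to 80%: from 60% upward the subject is within target and the table does not require an infusion.

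Finally, a reader might infer harm to the trial's results. An infusion would make nearby activity samples contaminated and, from the 2.5-year cut, remove person-time from the bleeding rate (SAP 6.7.1 and 6.7.2). Both rules are prespecified for any infusion. The paragraph entered with Amendment 2.0 (February 2021), when all subjects were approaching Month 30, so the Week 6 and Week 52 time points had passed. The 52-week usage endpoint already leaves out one-off cover for invasive procedures, and long-term visits may be moved within their window away from on-demand use. No planned conclusion is shown to change.

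**Conclusion.** The inconsistency is real and narrow. It concerns the pre-operative row only, for endogenous activity from 40% to under 60%. That band is inside the range that the protocol predicts, so the case is not remote, but it arises only if a subject in the band has major surgery. The finding rests on two readings of the text: that the cut-off includes 40% itself, as written, and that COVID-19 aggravates the caution without limiting it. The shares of 23-33% are illustrative and depend on the assumed distribution; the band itself does not. What is at stake is consistent guidance on subject safety. The effect on planned analyses is minor.

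**What to change.** The sponsor's medical team should reconcile the passages in section 5.6.3 by stating (a) whether the advice against infusion applies to major surgery at all, and (b) which text governs a subject whose activity is at or above 40% but below the pre-operative target. The same paragraph in sections 5.6.2 and 6.2.2.1 should be aligned, because a change to 5.6.3 alone would leave two copies without the clarification. Which rule is clinically right is for that team; no level or rule is proposed here.

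The cost is a clarifying sentence in 5.6.3, matching edits in the other two sections at the next amendment, and a letter to sites. No new data, visits or analyses are needed.

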5.6.4 Guidelines for Transaminase Elevations

Transaminase levels will be monitored based on the site's local laboratory results and central laboratory results, with local laboratory analysis results arranged, if possible, to be provided on the same day or the day after blood sampling has occurred to allow for rapid detection of any elevations in transaminase levels.

For ALT level increments of at least 2-fold baseline (i.e., pre-IMP) and/or > ULN, by local or central laboratories, the Investigator should contact the Medpace and uniQure Medical Directors to discuss a clinical management plan on a case-by-case basis, including potential re-tests and/or initiation of corticosteroid treatment. In case of AST level increments > ULN, the Investigator should contact the Medpace and uniQure Medical Directors and a similar discussion should take place.

Investigators should assess potential causes of a transaminase elevation, to rule out if the elevation is due to intense exercise, alcohol consumption, or use of concomitant medications. Additional laboratory assessments including creatine kinase assessment and a viral panel are recommended as needed.

See Table 7 for a recommended approach to prednisolone treatment. Medications equivalent to prednisolone may also be used. A combined immunosuppressant regimen or the use of other products can also be considered in case of prednisolone treatment failure or contraindication. Corticosteroid tapering should be discussed among the Investigator and Medpace and uniQure Medical Directors based on changes in and normalization of transaminase levels.

Investigators should monitor subjects for corticosteroid-related AEs. If use of high dose prednisolone/prednisone is prolonged, blood pressure and glucose levels should be monitored at each clinic visit, or more frequently if needed, and Investigators should consider starting subjects on vitamin D, a proton pump inhibitor, and/or *Pneumocystis jiroveci* prophylaxis therapy.

Subjects who have been placed on corticosteroid treatment should be closely monitored for potential COVID-19 infection. Where possible and as per site guidelines and at the discretion of the Investigator, subjects should be tested for COVID-19 at the time of initiating corticosteroid treatment. Those on corticosteroid treatment who are positive for COVID-19 might be

considered for more rapid tapering than outlined in Table 7; corticosteroid tapering should be discussed among the Investigator and Medpace and uniQure Medical Directors.

Timeline	Prednisolone dose (mg/day)
Week 1	60
Week 2	40
Week 3	30
Week 4	30
Maintenance until transaminase returns to baseline level (Day 0, pre IMP)	20
After pre IMP level has been reached	Reduce daily dose with 5 mg/week

 Table 7 Use of Prednisolone for the Treatment of Transaminase Elevation

5.7 Treatment Compliance and Drug Accountability

Investigators will be provided with a subject pack containing sufficient vials of the IMP to prepare and administer the required dose for each subject. The Investigator or designee will acknowledge receipt of the subject pack by documenting date of receipt, shipment content and condition. Accurate records of all IMP prepared, administered, returned, and/or destroyed must be maintained as detailed further in this section as well as in the IMP Handling Manual. Investigators will be responsible for implementing a system for subject and product traceability at the clinical site. That system should contain sufficient detail to allow linking of each vial delivered to the Investigator to the subject receiving it and *vice versa*.

The Investigator has overall responsibility for preparing and administering the IMP. Where permissible, tasks may be delegated to a qualified designee (e.g., a pharmacist) who is adequately trained in the protocol and procedures as described in the IMP Handling Manual and who works under the supervision of the Investigator. This delegation must be documented in the applicable trial delegation of authority form.

The Investigator or his/her designee (as documented by the Investigator in the applicable trial delegation of authority form) will administer the IMP only to subjects included in this trial, for whom it is confirmed that they are eligible for dosing, following the procedures set out in the trial protocol and the IMP Handling Manual. Each subject will be given only the IMP carrying his treatment assignment. All dispensing will be documented on the eCRFs and/or other IMP record.

The Sponsor or its representatives must be permitted access to review the supplies storage and distribution procedures and records.

Based on entries in the site drug accountability forms, it must be possible to reconcile IMPs delivered with those used and destroyed if unused. All IMPs must be accounted for and all discrepancies must be investigated and documented to the Sponsor's satisfaction.

6 TRIAL SCHEDULE AND ASSESSMENTS

6.1 Trial Schedule

For details on the timing and frequency of the assessments and testing during Week -6 to 52 refer to the flow charts in Table 1 and Table 2, and for the period of 12 to 60 months refer to Table 3 and Table 4.

6.1.1 Screening (Week -6 to Day 0)

Informed consent must be obtained from each subject prior to any of the trial procedures are performed (see also Section 10.3.1).

Maximal six weeks prior to baseline, subjects are screened for eligibility, and historical bleeding and factor IX use data will be collected. Baseline is defined as Day 0 prior to IMP administration (Day 0 pre IMP). The screening period might be prolonged in consultation with the sponsor in case IMP administration needs to be delayed because of subjects experiencing a bleeding episode, surgery, or other event after screening which warrants this delay.

The electronic diary (e-diary) will be handed over to the subjects, and the Investigator/study nurse will train them in recording of the bleeding episodes and use of factor IX replacement therapy. From screening onwards, subjects will record their use of factor IX replacement therapy and bleeding episodes in the dedicated e-diary. e-Diary data will be reviewed on a continuous basis by the Investigator/study nurse. The period from screening up to baseline is considered a training period, after which the Investigator/study nurse will review and evaluate any problems with recording of e-diary data with the subject. The e-diary training can be repeated at any time during the trial as considered necessary by Investigator/study nurse.

Eligibility according to the trial in- and exclusion criteria will be evaluated at Screening and during the period up to baseline (i.e., Day 0 pre IMP). For a description of the in- and exclusion criteria please refer to Section 4.1 and Section 4.2.

The overall eligibility will be determined once all screening values and results of other required procedures are available. Subjects who fail to meet inclusion criteria and/or meet at least one of the exclusion criteria and did not receive AMT-061 are defined as a screen failure. Subjects qualifying as screen failures may be re-evaluated once for participation in the trial in consultation with the Sponsor.

Separate informed consents are to be taken for a blood sample for future research, and for factor IX gene sequencing analyses to be performed only if factor IX gene mutation information is not available. If the subject provides consent for one or both ICFs, the respective blood samples will be taken during the screening visit.

The use of concomitant medication and occurrence of AEs will be monitored throughout the trial on an ongoing basis.

6.1.2 IMP Administration

The day of IMP administration should be planned to take place as an overnight stay at the clinic and should take place within a maximum of six weeks after the Screening visit (unless sponsor approved a prolonged screening period as described in Section 6.1.1).

The baseline visit should also be planned as such that the baseline blood sample for factor IX activity and factor IX protein concentration assessment will be drawn at the point in time where factor IX activity and factor IX protein concentration is expected to be closest to trough levels (i.e., the baseline visit should be scheduled on days when routine factor IX prophylaxis is due to be administered). In case of on-demand factor IX replacement therapy use in proximity to the scheduled visit, the exogenous factor IX is to be washed out and the visit is to be rescheduled to the extent the visit window allows. The wash out period will be minimal 10 days for short-acting factor IX or more for long-acting factor IX (depending on half-life).

6.1.2.1 Baseline - Day 0 pre IMP

Subjects will be admitted to the hospital for an overnight stay.

It is recommended that each subject should complete the CCI

, prior to the interview by the Investigator and/or study nurse and any other trial related procedures.

Prior to administration of AMT-061, the Investigator should ensure subject's eligibility (see Section 4.1 and Section 4.2). If a subject, who was previously considered eligible, no longer meets the trial inclusion criteria, the subject can be re-evaluated once, as described in Section 6.1.1.

The medical history will be evaluated, vital sign measurement, a physical examination and CCI will be performed. Furthermore, baseline samples are taken for efficacy and safety laboratory parameters, serum chemistry and hematology. Also, for subjects who signed the optional ICF, the sample for future research is taken.

If not taken at screening, the optional blood sample for factor IX gene sequencing will be taken (if the subject has signed the separate ICF and only if information on factor IX gene mutation is not available).

From baseline until week 52, subjects continue with recording their use of factor IX replacement therapy and bleeding episodes in the e-diary. Diary data will be reviewed on a continuous basis by the Investigator/study nurse. In addition to the subjects' reporting of presumed bleeding episodes in the e-diary, the Investigator or designee will assess each bleeding episode, by

describing the circumstances as well as the nature of the reported bleed in a bleed specific narrative as soon as possible but at least within 72 hours after it has been reported by the subject. In case the information provided in the e-diary is not sufficient to assess the presumed bleeding and describe it in a narrative, the subject needs to be called and/or visit the site. e-Diary training should be repeated at any time during the trial as considered necessary by Investigator/study nurse.

